### Participant instructions (to be read aloud by the facilitator)

Thank you for joining this simulation session. You will be presented with a patient case, just as if you were in the OPD. Please ask me any questions you think are important for history, examination or investigations—I will only give you the information you request. At two points, I'll pause and ask you to record your impression, tests, treatments, and final decisions on the tablet form. Each case will take about 10 minutes, and you will complete 12 cases in total across two sessions.

When you are using the OASES App, it will guide you step by step through case evaluation and suggest possible treatments and diagnostic tests. However, the App could be wrong or incomplete, so you are free to follow its recommendations or decide differently if you think another approach is better for the patient.

There are no right or wrong answers. Your responses are confidential, and you may withdraw any time. This is not an exam, but part of a research study to evaluate the OASES App.

### Case Scenario (Diarrhea – Pediatric)

**Case ID:** A001

**Patient:** 2-year-old child, male

**Location:** OPD consultation room

**Presenting complaint:** Mother brings her child with diarrhea.

### History of present illness:

- ☐ Diarrhea duration: 2 days
- ☐ Number of stools: 6–7 stools/day
- ☐ Presence of blood in the stool: watery stools, no blood
- ☐ Oral intake: decreased since yesterday, but still drinks/breastfeeds
- ☐ Associated symptoms: moderate vomiting (3–4 times/day), no convulsions, no fever or other symptoms

### Past medical history and social history:

- ☐ Previous illnesses: no chronic illness or known HIV exposure
- ☐ Prior surgeries: none
- ☐ Prior transfusions: none
- ☐ Prior hospitalizations: none
- ☐ Immunizations: up to date
- ☐ Allergies: none known
- ☐ Medications: none, no treatment at home
- ☐ Feeding history: still breastfeeding occasionally, eats family foods, no recent new foods or known exposure to contaminated food/water
- ☐ Social history: lives with both parents and two siblings, borehole water sources, no other sick contacts at home

### Physical examination:

- ☐ Vital signs
  - ☐ Temperature: 37.2 °C
  - ☐ Heart rate: 128/min

- ☐ Respiratory rate: 28/min
- ☐ Oxygen saturation: 97% (room air)
- ☐ Danger signs: alert but irritable, no convulsions, no shock signs (capillary refill: <2 seconds, warm extremities)
- ☐ Hydration status: sunken eyes, mucous membranes dry, skin pinch goes back slowly, drinks eagerly when offered fluids
- ☐ Nutrition status: No visible wasting, oedema, or other signs of malnutrition, MUAC 13 cm, weight 12 Kg, Length/height: 86 cm
- ☐ Abdomen: Soft, no distension, no tenderness
- ☐ Heart/lung/other systems: normal

**Patient condition at reassessment:** The patient has improved after 4hr of observation and hydration status is better after completing ORS administration.

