### C.7. Intervention and Control

Experimental arm (OASES App): Participants will use the OASES tablet-based CDSS, which incorporates the Interagency Integrated Triage Tool (IITT) and three condition-specific algorithms (diarrhea, dyspnea, and seizures) derived from WHO and Uganda Clinical Guidelines. No formal training sessions will be conducted; however, participants will receive a brief orientation walk-through of the App immediately prior to its use.

Control arm (standard practice): Participants will manage simulated cases without the App, relying on their usual knowledge and clinical experience. Standard resources available in OPD, including paper-based versions of the IITT and Uganda Clinical Guidelines, will be available for reference.

All participants will complete both arms using a crossover design, with a washout period of at least one week between conditions. During the washout, participants will return to their normal OPD duties without access to the OASES App. No additional clinical teaching or training will be provided during the study period.

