### C.8. Simulation and Scenarios

Each participant will complete 12 facilitated clinical vignette scenarios, with six scenarios per study arm (two diarrhea, two dyspnea, and two seizures). Scenarios will be adapted from WHO training materials for emergency care (e.g., *Basic Emergency Care* course, *Emergency Triage Assessment and Treatment* guidelines) and tailored to reflect common emergency presentations in the OPD of [name] Hospital. Both adult and pediatric cases will be included, varying in severity and presentation to capture the spectrum of conditions typically encountered. Draft cases will undergo expert review and pilot testing with representative clinicians to ensure clarity, realism, and contextual relevance. Cases will be designed in matched pairs to ensure comparable content and difficulty between study periods, with equivalence determined by expert review and pilot testing. Scenarios will be balanced for complexity, number of critical actions, and expected completion time.

Cases will be delivered verbally by a trained facilitator, who will respond only to participant questions to simulate real-world information gathering. Facilitators will log which key history and examination items are elicited using a structured tick-box script.

At two predefined points in each vignette, participants will record their diagnostic and treatment plan:

1. Initial assessment stage – working impression, immediate treatments, and diagnostic tests ordered.
2. Post-investigation stage – final diagnosis, disposition decision, treatment plan and follow-up plan.

Each participant's simulation session will last approximately one hour. All sessions will be scheduled during off-duty hours to ensure voluntary participation and to avoid disruption of patient care.

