### C.9. Outcomes

Primary outcome:

- Guideline-adherent management: Proportion of pre-specified, guideline-consistent critical management actions (diagnostics and treatments) completed per vignette (proportion 0-1). Participant responses recorded at the initial assessment and post-investigation stages will be scored against a gold-standard answer key derived from WHO guidelines (Basic Emergency Care assessment checklists, ETAT performance checklists, Integrated Management of Childhood Illness checklists). Scoring will be performed by two independent assessors, blinded to allocations, mapping free text to binary items (performed correctly vs. not performed/incorrect). Disagreements will be resolved by consensus.

Secondary Outcomes:

- Triage accuracy: Correct assignment to Interagency Integrated Triage Tool (IITT) category (Red/Emergency, Yellow/Urgent, Green/Non-urgent) compared with the case-specific expected category (binary). Scoring will be performed by two independent assessors, blinded to allocations.
- Disposition appropriateness: Appropriateness of the disposition decision (hospitalize, discharge) compared with case-specific expected disposition in the answer key, based on

WHO/Uganda guidelines (binary). Scoring will be performed by two independent assessors, blinded to allocations.

- Diagnostic accuracy: Correctness of working impression (initial stage) and final diagnosis (post-investigation stage), compared with case-specific diagnostic labels in the answer key, based on WHO/Uganda guidelines (binary). Scoring will be performed by two independent assessors, blinded to allocations, mapping free text to binary items (performed correctly vs. not performed/incorrect).
- Guideline-adherent evaluation (process quality): Proportion of critical history and examination items elicited by the participant during the vignette, compared with case-specific list of critical items derived from WHO guidelines (proportion 0-1). Scoring will be performed by two facilitators during each simulation session using the facilitator tick-box logs.
- Time to completion: Duration needed to complete each vignette, measured by facilitators (continuous).
- Usability: Total score on System Usability Scale (SUS), a widely validated 10-item tool for evaluating software systems in healthcare and other fields (continuous).

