## Appendix C. Case Script and Facilitator Tick-Box Checklist (Sample: Diarrhea – Pediatric)

### Facilitator instructions:

- Provide information only when the participant asks.
- Do not volunteer information unless explicitly prompted.
- Tick each item when it is asked about.
- Critical WHO-required actions are underscored.

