**Test results (only if requested):**

- ☐ RBS: normal
- ☐ CBC: normal
- ☐ Malaria (MRDT and B/S): negative
- ☐ Stool culture: normal
- ☐ Abdomen x-ray: negative
- ☐ Chest x-ray: negative
- ☐ Other labs/diagnostics if asked: normal

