### Example Case (A001: Pediatric Diarrhea)

Patient: 12 years, 12 kg, MUAC 13 cm, watery diarrhea, vomiting, some dehydration, no danger signs

Gold Standards:

- Triage Category: Yellow (Urgent; some dehydration, no danger signs)
- Immediate Treatments: Only Plan B rehydration: ORS  $\approx 75$  mL/kg ( $\approx 900$  mL) over 4 hours, small frequent sips, reassess at 4 h; continue breastfeeding
- Investigations: None (child alert, afebrile, no severe dehydration, no red flags), malaria test (MRDT or B/S) acceptable in Kalongo due to local epidemiology
- Diagnosis: Diarrhea with some dehydration (acceptable: "acute watery diarrhea," "AWD," "viral gastroenteritis with some dehydration")
- Disposition: Discharge
- Treatment Plan: No antibiotics (no blood in stool, no cholera outbreak); supportive therapy such as paracetamol if febrile acceptable
- Follow-up Plan: since patient has improved after 4 hr observation, discharge with plan A = extra fluids, continue feeding/breastfeeding, return precautions (worsening dehydration, blood in stool, persistent vomiting, convulsions, lethargy, inability to drink); optional zinc supplements (not available in Kalongo)

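### The A001 reassessment text says ORS was completed and worked whatever the participant ordered, and so cues scored Stage 2 answers; the trial-wide effect is small unless other scripts do the same

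*Combined protocol and SAP*

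**What the plan says.** Section C.8 has participants record answers at two points. The first is "Initial assessment stage – working impression, immediate treatments, and diagnostic tests ordered". The second covers "final diagnosis, disposition decision, treatment plan and follow-up plan". Under C.9 both count: "Participant responses recorded at the initial assessment and post-investigation stages will be scored against a gold-standard answer key". The primary outcome is the share of critical diagnostic and treatment actions completed per vignette; disposition and diagnosis are separate secondary outcomes.

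The Appendix C script for A001 ends its physical examination part with a reassessment line: "The patient has improved after 4hr of observation and hydration status is better after completing ORS administration". It is the only reassessment text shown. It has no branch by what was ordered, no release condition of the kind attached to the test results, and no link to a stage. The general facilitator rule is "Do not volunteer information unless explicitly prompted".

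In the Appendix E key for A001, ORS belongs to the first-stage item: "Immediate Treatments: Only Plan B rehydration", followed by volume, timing and delivery. The Stage 2 keys cover the absence of antibiotics, discharge, extra fluids, feeding and return precautions. The follow-up key gives the improvement after the observation period as its reason.

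**The concern.** A participant who wrote no ORS at Stage 1, or wrote something else, is told that ORS was given, finished and effective. That contradicts the course their own orders would imply. It also names a keyed treatment, the observation interval and the hydration problem before scored free text is written. Each period contains two diarrhea cases in random order, so the same information may also reach a later diarrhea case in that period or the next.

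The trial measures whether the App supplies knowledge that clinicians otherwise lack. A cue from the facilitator that supplies part of it to everyone blurs that contrast. The planned analyses do not undo this. Period and sequence terms adjust for shifts between sessions, and the first-exposure analysis drops the second session, but a cue inside a vignette is still present in the first session.

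**Working it through.** **Step 1: is the line meant to be known before Stage 2?** The documents do not say when it is read, or to whom. The follow-up key takes the reported improvement as given, so a participant without that information could not be expected to reach the keyed answer. Knowledge of it before Stage 2 is a fair inference, but not a stated rule.

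**Step 2: which scored items can it reach?**
- *Treatment and follow-up plan* (Stage 2, primary score): reached, since ORS and hydration are named before this is written.
- *Immediate Treatments* (Stage 1, primary score): reached only if Stage 1 stays editable or a late entry is credited. No section locks Stage 1, and the Appendix E assessor instructions do not tie this item to Stage 1 text, so neither is excluded.
- *Disposition* (secondary): cued by the improvement, not by the naming of ORS.
- *Diagnosis* (secondary): weakly cued, because the key also accepts labels that do not mention dehydration.

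**Step 3: the plan's own count.** C.4: 16 participants × 12 scenarios = 192 vignettes, which reproduces the stated figure. Each participant meets A001 once, so it supplies 16/192 = 1/12 = 8.3% of vignettes.

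**Step 4: size.** The documents give no item success rates and no cue effect, so what follows is an assumption range. Let p be the success rate on an item without the cue, and L the chance that the cue turns a wrong answer into a right one. The credited rate is p + L(1 − p). With the same L in both arms, the item difference becomes (1 − L) times its uncued size. I assume three primary items per case (immediate treatments, investigations, treatment and follow-up plan), equal item differences, equal case weights, and a comparison on the proportion scale.

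- One item exposed, within A001: shrinkage L/3.
- One item exposed, A001 the only such case of 12: L/36.
- Two items exposed (late ORS credited), A001 only: 2L/36.
- All 12 scripts with such a line: L/3 (one item) or 2L/3 (two items).

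| L | A001 itself, 1 item | Trial, A001 only, 1 item | Trial, A001 only, 2 items | Trial, all 12, 1 item | Trial, all 12, 2 items |
|---|---|---|---|---|---|
| 0.25 | 8.3% | 0.7% | 1.4% | 8.3% | 16.7% |
| 0.50 | 16.7% | 1.4% | 2.8% | 16.7% | 33.3% |
| 1.00 | 33.3% | 2.8% | 5.6% | 33.3% | 66.7% |

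For example, an assumed trial-wide difference of 0.200 becomes 0.194 at L = 1 with one item exposed in A001 only (0.200 × 35/36).

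**Step 5: direction.** Let L differ by arm, with assumed uncued rates of 0.40 (control) and 0.60 (App), a difference of 0.20.
- L = 0.25 control, 0.50 App: 0.40 + 0.25 × 0.60 = 0.55 and 0.60 + 0.50 × 0.40 = 0.80. The item difference rises to 0.25.
- L = 0.50 control, 0.25 App: 0.40 + 0.50 × 0.60 = 0.70 and 0.60 + 0.25 × 0.40 = 0.70. The item difference falls to 0.00.

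Attenuation follows from equal uptake; without that assumption the direction is open.

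**The case against.** The best defense is that the line gives away little that is scored. ORS is keyed to a field answered at Stage 1. The Appendix E instructions also require the right plan, the amount, and how it is given and rechecked, with needless treatments avoided, and they forbid reading in what was not written. The line supplies no plan, amount or method of giving. A fixed course also keeps the case identical for everyone against one key, and the improvement that cues discharge belongs to that course. Facilitators are told not to volunteer information, so it is not certain that everyone hears the line. Only a sample script is shown.

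Most of this stands, and it limits the size. It does not remove the mismatch with a participant's own orders, or the naming of a keyed treatment before the Stage 2 plan. If the line is given only on request, exposure differs between participants, which is no better controlled.

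Three stronger readings are tempting and not supported:
- *The line repairs the ORS item and so removes much of the App effect.* This needs late credit, which is not stated, and an uptake rate that the documents do not give.
- *The effect is necessarily biased toward zero.* Step 5 shows otherwise.
- *The line breaches the C.7 statement that* "No additional clinical teaching or training will be provided during the study period". That sentence concerns instruction; a scripted patient course is case content. Learning between periods is already addressed by the washout, the period and sequence terms, and the first-exposure analysis.

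**Conclusion.** The point holds in a limited form. The A001 text is unconditional, can contradict what the participant ordered, and places keyed treatment content ahead of scored Stage 2 answers and later diarrhea cases. With equal uptake in both arms it is likely to attenuate the App-control difference, but neither direction nor size can be established from the documents.

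For A001 alone the trial-wide primary difference shrinks by at most about 2.8%, or 5.6% if late ORS is credited. Those ceilings assume that every wrong answer on an exposed item is corrected, with equal uptake and equal weights. The effect becomes material only if the 11 scripts not shown carry similar lines, which is unknown. This is worth correcting because it is avoidable and cheap, not because A001 by itself threatens the primary result.

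**What to change.** In A001, and in any of the other 11 scripts written the same way:

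1. Replace the sentence with a treatment-neutral list of findings at the reassessment time point, naming no treatment and not saying that one was completed.
2. Release it in identical form to every participant, only after the Stage 1 form has been submitted and locked in Kobo Toolbox, and state this in C.8 and the facilitator instructions.
3. State in C.9 and Appendix E that Immediate Treatments is scored from Stage 1 entries only.
4. Reconcile the new text with the Appendix E follow-up key that depends on the reported improvement. No view is taken here on the clinical content of either.

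The improvement will still cue disposition; that is part of the fixed case course and should be acknowledged when that outcome is interpreted. The cost is one reworded passage per affected script, a form setting, two clarifying sentences and a read-through of the remaining scripts, which can be done within the expert review and pilot testing already planned in C.8. No extra participants, staff or session time are needed.

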**Test results (only if requested):**

- ☐ RBS: normal
- ☐ CBC: normal
- ☐ Malaria (MRDT and B/S): negative
- ☐ Stool culture: normal
- ☐ Abdomen x-ray: negative
- ☐ Chest x-ray: negative
- ☐ Other labs/diagnostics if asked: normal

**Facilitator Summary (to be entered in Kobo Toolbox at the end of the simulation session):**

- Participant ID: (assigned after randomization)
- Case ID:
- Case start time:
- Case end time:
- Guideline-adherent evaluation score (n° of ticked underscored items): \_\_\_\_/8
- Notes/comments:

## **Appendix D. Participant Response Form**

- Participant ID: (assigned after randomization)
- Case ID:

### **Stage 1 – Initial Assessment**

- Triage Category (according to IIT criteria):
  - Red (Emergency)
  - Yellow (Urgent)
  - Green (non-urgent)
- What is your working impression based on this initial evaluation? (free text)
- Which treatments would you start immediately? (free text)
- Which diagnostic tests would you request at this stage? (free text)

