### **Stage 2 – Post-Investigation Assessment**

- What is your final diagnosis after results? (free text)
- Disposition decision
  - Hospitalize
  - Discharge
- What is your treatment and follow-up plan for the patient? (free text)

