## Appendix E. Scoring Checklist for External Assessor with Gold Standard

### External Assessor Instruction:

Task: evaluate participants' responses in Kobo Toolbox against the gold-standard checklist for each case scenario. Score according to WHO and Uganda Clinical Guidelines.

How to score:

- Flag each item where the participant's response matches or is clinically equivalent to the gold standard.
- Leave blank if the response is absent, incorrect, or inappropriate.
- Do not infer beyond what is explicitly written by the participant.

Domains:

- Diagnostics: Correct if all indicated tests are ordered and unnecessary tests are avoided.
- Treatments: Correct if the participant specifies the correct plan, dose/volume, delivery/reassessment, and avoids harmful or unnecessary therapies.
- Diagnosis, triage, and disposition: Correct if the participant's answer matches the gold-standard label/category for the scenario.

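### The response form does not ask for the treatment detail that the scoring rule requires, so a correct but brief answer can score zero on a primary-outcome item

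*Combined protocol and SAP*

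**What the plan says.** **What participants are asked.** Appendix D, Stage 1 asks "Which treatments would you start immediately? (free text". Stage 2 asks "What is your treatment and follow-up plan for the patient? (free text". The script in Appendix C tells participants that at two points "I'll pause and ask you to record your impression, tests, treatments, and final decisions on the tablet form". None of the three asks for dose, volume, manner of giving or time of reassessment.

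**What assessors score.** The External Assessor Instruction in Appendix E reads "Treatments: Correct if the participant specifies the correct plan, dose/volume, delivery/reassessment, and avoids harmful or unnecessary therapies". It adds "Do not infer beyond what is explicitly written by the participant", but also "Flag each item where the participant's response matches or is clinically equivalent to the gold standard". In the one worked key (case A001), the Immediate Treatments entry gives a volume and continues "over 4 hours, small frequent sips, reassess at 4 h; continue breastfeeding".

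**Where the score goes.** Section C.9 defines the primary outcome as the proportion of critical diagnostic and treatment actions completed per vignette, with free text mapped to binary items. Section C.11 makes the crossover analysis of that outcome the only confirmatory one.

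**What each arm has to hand.** The script says of the App that "it will guide you step by step through case evaluation and suggest possible treatments and diagnostic tests". Section C.7 gives control participants paper copies of the triage tool and the national guidelines.

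**The concern.** The instrument that collects the primary outcome and the instrument that scores it ask for different things. A participant who answers the Stage 1 question fully as put may omit everything the treatment rule needs beyond the name of the treatment. Section C.11 justifies scoring blanks as incorrect by taking an unanswered item to show lack of knowledge or failure to act. That reasoning does not carry over to detail that nobody requested.

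Two consequences are possible. First, scores in both arms may be too low, which would distort the preliminary estimates that Section C.4 intends for planning the next trial. Second, if one arm writes more detail than the other, part of the App–control difference would reflect how fully people wrote rather than how they would manage the patient.

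The planned safeguards do not reach this. Blinded assessors see only the text, so they cannot restore what was not written. Consensus and adjudication work on the same text. The first-exposure analysis uses the same form and the same key.

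**Working it through.** **Plan figures.** The plan gives no figure for this point. Its sample size reproduces: 16 participants × 12 scenarios = 192 observations. The A001 key agrees with its own inputs: 75 mL/kg × 12 kg = 900 mL. Neither is in dispute.

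**Step 1: form against key, case A001.**

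| Element under Immediate Treatments | In the key | Requested by Stage 1 or script |
|---|---|---|
| Treatment or plan | yes | yes |
| Volume | yes | no |
| Duration and manner of giving | yes | no |
| Reassessment | yes | no |

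The Stage 2 entries for A001 concern antibiotics, home fluids, feeding and return advice. They require no dose or volume. On the only key shown, the box clearly affected is Immediate Treatments.

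**Step 2: weight of that box.** The assessor sheet in Appendix E lists six boxes under guideline-adherent management, so the weight is 1/6. If only the diagnostic and treatment boxes count, as the wording of C.9 suggests (Immediate Treatments, Investigations, Treatment and follow-up plan), the weight is 1/3.

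**Step 3: size, on assumed inputs.** Let *d* be the between-arm difference in the share of all vignettes in which the box loses credit only because detail was not written. The documents give no value for *d*, so a range is used.

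Shift in mean primary score = (affected boxes ÷ boxes scored) × *d*

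| *d* (assumed) | 1 of 6 boxes | 1 of 3 boxes |
|---|---|---|
| 0.10 | 0.017 | 0.033 |
| 0.20 | 0.033 | 0.067 |
| 0.30 | 0.050 | 0.100 |
| 0.50 | 0.083 | 0.167 |

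For example, 0.50 × 1/6 = 0.083 and 0.50 × 1/3 = 0.167. The arithmetic ceiling (*d* = 1) is 0.167 or 0.333. If keys that are not shown also require detail in the Stage 2 treatment box, the shifts double. If *d* is instead measured only among participants who chose the right treatment, the shift shrinks in proportion to their share. The formula gives size only: the sign of *d* is not known, and *d* = 0 gives no bias in the contrast.

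**The case against.** A reader might infer that App users can copy doses and volumes from the screen while controls cannot, so that the bias favours the App. The documents do not support this. They say that the App guides users through treatment steps and suggests treatments; they do not say that it displays dose or volume. Controls have paper guidelines to copy from, and both arms receive the same form and script. A favourable direction for the App is a possibility, not a finding.

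A reader might also infer that a brief answer is certain to be marked wrong. That is too strong. Assessors are told to accept equivalent answers, Plan B is the key's own label, and the slashes in the treatment rule may mark alternatives. What stands is that the equivalence rule sits beside an explicit requirement for detail and a ban on inference, so two assessors could treat the same answer differently. The planned Cohen's κ may show such disagreement but cannot recover missing text.

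Two further objections have force. Specifying the right volume is a legitimate part of adherence, and a decision-support tool that leads clinicians to specify it is partly doing its job; not all of a difference in detail would be spurious. The open prompt is also consistent with a design that gives information only when asked (Section C.8), and a prompt that names scored content would cue it and could narrow the contrast. Both objections bear on how to repair the mismatch. Neither explains why detail should be scored without being requested.

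**Conclusion.** The mismatch between Appendix D and Appendix E is plain from the text and touches the only confirmatory outcome. A correct but brief treatment answer can score zero on a primary-outcome item, depending on how the assessor reads the equivalence rule. This can depress scores in both arms. Whether it biases the App–control contrast, in which direction and by how much, cannot be determined from the documents.

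The illustrative range of about 2 to 8 points, or 3 to 17 points, rests on an assumed 10 to 50 point between-arm difference, on one affected box, and on the A001 key being typical of the other cases, whose keys are not shown.

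This should be fixed before sessions start, because detail that was never collected cannot be recovered at scoring. In a feasibility-sized pilot it does not by itself invalidate the design.

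**What to change.** 1. Add one neutral instruction to the Appendix D treatment fields and to the Appendix C script, worded identically for both arms. For example: *for each treatment, state the dose or volume and how it would be given*. Do not name scored content such as the time of reassessment or the return advice, since that would cue the answer.
2. In Appendix E, score the choice of treatment and the dose and delivery detail as separate binary items. A short answer then earns the first item and not the second, which settles how the equivalence rule applies to it and makes any between-arm difference in written detail visible. Elements left unprompted, such as reassessment, should not decide the choice item.
3. State before scoring which items enter the primary proportion, because splitting a box changes the denominator.

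The clinical content of the key stays as it is, and the 16 participants and 192 observations are unaffected. The cost is a wording change to the form and script, slightly more typing in both arms, a few more items to score, and a possible small rise in control scores.
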